8.1. Study Overview

This post market clinical evaluation is a prospective, randomized post-market assessment. Each eligible subject will receive a single lumen PICC device and will be placed per the manufacturer's IFU and in accordance with institutional policy.

Per institution policy, due to the fact that the HydroPICC is not a standard of care device, the patient will be consented prior to insertion. This consent will follow the institution's standard of care policies.

any patient receiving a single lumen PICC will be approached to join this study. After the patient consents, and the site reviews the inclusion criteria, the subject can be randomized.

Screening data will be reviewed to determine subject eligibility. Subjects who meet all inclusion criteria and none of the exclusion criteria will be entered into the study. There is an exclusion criteria which requires an ultrasound, and a subject can still be screen failed at the time of insertion.

The following treatments will be used:

AVI device: Access Vascular HydroPICC Single Lumen PICC

Comparator device: [REDACTED] Single Lumen PICC

Vein: Preference is Basilic Vein followed by Brachial Vein, then Cephalic Vein

Once a subject is inserted with a PICC line, they are considered enrolled.

Total duration of subject participation will be the duration for which the catheter is indwelling in the patient up to 16 days. The total study duration is expected to not exceed 23 days, including procedural pre-screen. Insertion of the PICCs will be prioritized with the following: Basilic vein then Brachial vein followed by Cephalic vein. Diagnosis of both asymptomatic and symptomatic vein thrombosis will be established by Doppler ultrasound examination. Examinations will be performed prior to device insertion to establish patient baselines.

[figure not shown]
Ultrasound will be performed pre-insertion of the device, at 7 days post-insertion (± 5 days) and 14 days (± 7 days). Data will be collected using a scale defined previously.

9. Study Methods and Measurements

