10.7. Enrollment

A subject is considered enrolled when the assigned PICC is inserted. Due to the current situation with COVID, the sponsor is concerned about lost to follow up rates. To prepare for this, the site will enroll 4 extra subjects bringing the total to 24. The plan is to analyze 10 enrolled subjects on each arm, but the site will recruit for 12 in case of COVID related follow up issues.

Screening process

A Prospective, Randomized PICC Asymptomatic Thrombosis Study (PROPATH)	Number: 20-002 Version: C 28Apr2021 Page: 17 of 30
---	---

11. Discontinued Subjects

If a subject is unable to complete the study for any reason, then the investigator will use the screen failed randomization envelope to recruit for this discontinued subject. Data from the discontinued subject will not be used for the per protocol analysis. However, demographics will be used for the recruitment analysis. Any subjects in section 12 described below will be replaced using the method mentioned in this paragraph.

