14.5. Unscheduled Visit(s)

1. Perform and record vital signs.
2. Record Adverse Events (if any).
3. Record changes to concomitant medications.
4. Record labs, if available.
5. Conduct ultrasound assessment of treatment extremity.
6. Take picture of insertion site.
7. Remove or treat the PICC line per IFU and institutional protocols if necessary.
8. If a subject is discontinued from the study due to a Serious Adverse Device Effect, the institution should notify their IRB per the IRB reporting requirements.

15. Adverse Event Reporting

These definitions are for the purposes of this post market clinical evaluation only. Medical Device Reporting (MDR) will be conducted using the normal AVI definitions for reporting to the FDA. We will follow [REDACTED].

Adverse Event (AE) (ISO 14155:2020): untoward medical occurrence, unintended disease or injury, or untoward clinical signs (including abnormal laboratory findings) in subjects, users or other persons, whether or not related to the investigational medical device and whether anticipated or unanticipated.

Note 1: This definition includes events related to the investigational medical device or the comparator.

Note 2: This definition includes events related to the procedures involved.

Note 3: For users or other persons, this definition is restricted to events related to the use of investigational medical devices or comparators.

Adverse Device Effect (ADE) (ISO 14155:2020): is an adverse event that is related to the use of an investigational medical device.

Note 1: This definition includes adverse events resulting from insufficient or inadequate instructions for use, deployment, implantation, installation or operation, or any malfunction of the investigational medical device.

Note 2: This definition includes any event resulting from use error or from intentional misuse of the investigational medical device.

Note 3: This includes "comparator" if the comparator is a medical device.

Comparator: medical device, therapy (e.g. active treatment, normal clinical practice), placebo or no treatment, used in the control group in a clinical investigation.

Serious Adverse Event (ISO 14155:2020):

A Serious Adverse Event (SAE) is an adverse event that:

- a) Led to death,
- b) Led to serious deterioration in the health of the subject, users, or other persons as defined by one or more of the following: 1) A life-threatening illness or injury, or

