16.1. General Considerations

Study data will be made available in listings or electronic files as needed. The study results will be reported in tabular form using descriptive statistics, confidence intervals, or statistical tests as indicated.

All summaries will be done by randomized treatment group. Numeric descriptive statistics include the n, mean, standard deviation (SD), median, minimum value, and maximum value. These will be calculated for all numeric baseline data. Categorical summaries will show the number and percent of subjects in the levels associated with the variable summarized and the analysis performed. Percentages will be calculated based on the total number of subjects with non-missing data for the assessment. The denominator should be included for each summary to indicate the set of subjects being summarized.

For any inferential analyses, a two-sided p-value of less than or equal to 0.05 will be considered statistically significant. Any confidence intervals provided will be two-sided 95% intervals. The primary effectiveness assessment is considered the primary analysis. This study is not intended to support claims and the other statistical tests included are intended to assist with reporting, hence, no other adjustment for multiplicity will be used.

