16.3. Analysis Populations

The primary analysis will be based on a Full Analysis Set (FAS) analysis population defined as those who were randomized and met all inclusion and exclusion criteria. A Per-Protocol (PP) population will be completed that excludes subjects who have one or more major protocol deviations. Major protocol deviations will be identified prior to locking the database for the final analysis and will include, but are not limited to, not receiving the randomized treatment, not completing the study, and not have met all inclusion and exclusion criteria. Information for subjects not in the FAS population will be listed if available.

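### Replacement and per-protocol rules make no exception for a PICC removed because of thrombosis, so an outcome event can remove its own case from the per-protocol set, mainly for the symptomatic endpoint

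*Combined protocol and SAP*

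**What the plan says.** **Replacement and PP exclusion.** On early leavers, Section 11 says: "If a subject is unable to complete the study for any reason, then the investigator will use the screen failed randomization envelope to recruit" a substitute. It continues: "Data from the discontinued subject will not be used for the per protocol analysis". Section 16.3 gives as examples of major deviations, which exclude a subject from PP, "not receiving the randomized treatment, not completing the study, and not have met all inclusion and exclusion criteria".

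**How an event can end participation.** Section 8.1: "Total duration of subject participation will be the duration for which the catheter is indwelling in the patient up to 16 days". Section 14.5 requires an ultrasound at an unscheduled visit and then allows staff to "Remove or treat the PICC line per IFU and institutional protocols if necessary".

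**Primary population.** Section 16.3: "The primary analysis will be based on a Full Analysis Set (FAS) analysis population defined as those who were randomized" and were eligible. Completion is not a condition. Section 11.5 keeps data gathered before withdrawal for the overall analysis.

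**Denominators and tests.** Section 16.1: "Percentages will be calculated based on the total number of subjects with non-missing data for the assessment". Section 16.5.1 tabulates grades at pre-insertion, post-insertion and the 7-day visit. It then tests the highest grade (Cochran-Armitage) and the presence of any asymptomatic thrombosis (Fisher). Section 16.5.2 treats the symptomatic endpoint the same way.

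**Numbers.** Sections 10.6 and 10.7 plan to analyse 10 per arm and enrol 12 per arm.

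**The concern.** Removal of the catheter is a plausible consequence of the event being measured. If removal counts as failure to complete, the rules in Sections 11 and 16.3 select on the outcome: a subject with the event leaves the PP set, and someone who kept the catheter takes the place. The remaining subjects then show a lower thrombosis rate than was true of those who received the device. The loss is larger in the arm with more removals, so the difference between arms tends to shrink.

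The symptomatic endpoint is most exposed, because symptoms prompt the unscheduled visit at which removal can occur. The study is unpowered, but Section 16.2 says its purpose is to see whether the ultrasound endpoint is feasible for a larger study. Event rates taken from subjects who kept their catheter would mislead that planning. The study is also unblinded (12.2). Any choice left open about whose scan counts would be made by people who know the arm.

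**Working it through.** **1. The plan's own figure.** 2 × 10 + 4 = 24 enrolled, or 12 per arm. This reproduces. The allowance is 2/12 = 16.7% loss per arm. Section 10.7 justifies it by COVID-related loss to follow-up, not by removals for thrombosis.

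**2. The chain of rules.** Unscheduled scan for a suspected event, then possible removal (14.5); participation ends with removal (8.1); the subject has not completed, so is replaced and excluded from PP (11, 16.3). The first and last links are explicit. That removal amounts to non-completion is an inference from 8.1. No visible passage confirms or excludes it.

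**3. Rate seen in completers.** Let p be the true rate and r the share of cases whose PICC is removed before completion, with no other losses. Completers show p(1 − r)/(1 − pr). Section 5.2 gives p = 3% to 20% for symptomatic thrombosis. The documents give no r, so a range is assumed.

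| r (assumed) | p = 20% | p = 3% |
|---|---|---|
| 25% | 0.15/0.95 = 15.8% | 0.0225/0.9925 = 2.3% |
| 50% | 0.10/0.90 = 11.1% | 0.015/0.985 = 1.5% |
| 100% | 0% | 0% |

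**4. Events lost per 12 subjects** = 12 × p × r. At 20%: 0.6, 1.2 and 2.4. At 3%: 0.09, 0.18 and 0.36.

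**5. Difference between arms.** If the arms sat at the two ends of that range (an assumption), the true difference is 17 points. With the same r in both arms it reads 15.8 − 2.3 = 13.5 points at r = 25%, and 11.1 − 1.5 = 9.6 points at r = 50%. Equal removal fractions do not protect the comparison.

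**6. Effect on the spare subjects.** The chance that removals alone exceed 2 of 12 is the binomial tail P(X ≥ 3) with probability pr. At p = 20% it is 2.0%, 11.1% and 44.2% for r = 25%, 50% and 100%.

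**7. The FAS.** The subject stays in by definition. Three points remain open:
- whether an unscheduled scan fills the 7-day row of the table;
- whether it enters the highest grade used in the trend test;
- whether a replaced subject is analysed at all, since 10 per arm cannot be a fixed number if replaced subjects also stay in the FAS.

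**The case against.** The strongest reply is that the primary analysis is not the one affected. The FAS does not require completion. Section 11.5 retains data before withdrawal. Sections 7.1 and 7.2 list unscheduled scans beside the scheduled ones, and both tests in 16.5.1 can be read at subject level. Visit 3 is 7 ± 5 days, so a scan on Day 5 falls inside its window (Days 2 to 12) and nothing bars its use there. All of this stands. For the FAS the fault is silence about which scans count, not certain deletion.

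A reader might infer that the asymptomatic primary rate, quoted at 48% in Section 6.1, is deflated in the same way. The documents do not support that. Section 5.2 defines asymptomatic thrombosis as an ultrasound finding without symptoms. Such cases are normally found at a scheduled scan and are counted there before any removal. Subjects removed for a symptomatic event are not asymptomatic cases. If a share s of the arm left the denominator for that reason, the asymptomatic rate would rise to p/(1 − s), for example 0.48/0.90 = 53% at an assumed s = 10%. The PP asymptomatic rate would fall only if scheduled-scan findings themselves led to removal, and the documents give no frequency for that.

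It is also fair that removal need not mean non-completion. Section 8.1 can be read as making removal the natural end of participation. Section 11.1 does not list removal among its discontinuation reasons, and it encourages remaining visits. Section 14.5 allows treatment as well as removal. This does not rescue the rule, because 8.1 and 11.1 pull in different directions and nothing settles the matter.

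Finally, this is an unpowered pilot that is not meant to support claims. Safety and failure endpoints are compared separately (16.5.3, 16.6), and the other endpoints are redacted. That limits the consequence but does not define the PP set.

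**Conclusion.** The point holds for the PP set, mainly for the symptomatic endpoint. As written, an outcome event can lead to its own subject's replacement and exclusion. A true 20% symptomatic rate would read as 15.8%, 11.1% or 0% if 25%, 50% or all cases were removed. At 3% the loss is under 0.4 events per 12 subjects. These figures assume that removal counts as non-completion, that there are no other losses, and that the removal fractions are as stated. The true size is unknown because the documents give no removal rate.

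For the FAS the finding is narrower. The subject is retained, but the plan does not say that an unscheduled scan counts in the visit table or in the highest grade, and the 10-per-arm target conflicts with a FAS that keeps replaced subjects. It would go too far to conclude that the primary asymptomatic comparison is biased downward.

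**What to change.** 1. In Sections 11 and 16.3, state that a subject with an inserted PICC whose participation ends because of thrombosis or device failure has reached an outcome. That subject has no major deviation for that reason, stays in both FAS and PP, and is not a non-completer to be replaced.
2. In Sections 16.5.1 and 16.5.2, define each subject's result as the highest grade on any scheduled or unscheduled scan up to removal, and keep these subjects in the denominators. Count symptomatic events in the symptomatic endpoint and in an added any-thrombosis summary, not as asymptomatic cases.
3. Reconcile Section 8.1 with 11.1 (participation ending at removal versus attending remaining visits), and Sections 10.6 and 10.7 with 16.3 (10 analysed per arm versus the FAS).
4. List every replaced subject by arm, reason and last scan.

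With this rule a true 20% stays 20% in expectation whatever the removal fraction. The cost is protocol and SAP wording. No new scan is needed, because 14.5 already requires one at the unscheduled visit, and clinical management does not change. The downside is that some results will come from scans outside the nominal visit, and the number analysed per arm may differ from 10.

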11.1. Early Discontinuation of Study Subject

A subject may be discontinued at any time if the subject, the investigator, or the Sponsor feels that it is not in the subject's best interest to continue. The following is a list of possible reasons for discontinuation:

- Subject withdrawal of consent
- Subject is not compliant with study procedures
- Protocol violation requiring discontinuation
- Sponsor request for early termination of study
- Positive pregnancy test (females)

All subjects who discontinue should come in for an early discontinuation visit as soon as possible and then should be encouraged to complete all remaining scheduled visits and procedures.

11.2. Lost to Follow-Up

The site should document at least 3 attempts to contact the subject before a subject is considered lost to follow-up. This will be documented in the end of study CRF.

11.3. Investigator Withdrawal

Investigators have the authority to withdraw a subject at any time, for any reason, specified or unspecified, and without prejudice. The investigator is requested to provide a reason for subject withdrawals. The reason for the subject's withdrawal from the study will be specified in the subject's source documents and recorded on the end of study CRF.

11.4. Subject's Withdrawal of Consent

All subjects are free to withdraw from participation at any time, for any reason, specified or unspecified, and without prejudice. Reasonable attempts will be made by the investigator to provide a reason for subject withdrawals. The reason for the subject's withdrawal from the study will be specified in the subject's source documents and recorded on the end of study CRF.

11.5. Use of Data Following Withdrawal

Data collected while the subject provided will be used for the overall analysis. No data will be collected or analyzed from the date that the subject withdrew from the study.

12. Study Treatment

12.1. Method of Assigning Subjects to Treatment Groups

The subjects will be randomized to the two different treatment groups. A match and replace method will be used to ensure that screen failed randomized subjects will be replaced appropriately. The randomization assignment methodology will be documented in the Statistical Analysis Plan.

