9.1. Methods Used to Minimize Bias and Maximize Validity

This study will be randomized using CONSORT guidelines stated below (www.consort-statement.org). The randomization will be conducted via sealed envelope. The specific randomization will be discussed in further detail below.

CONSORT 2010 Flow Diagram

10. Subject Selection

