10.6. Screen Failures

Any subject who signs an informed consent but fails to meet the required entry criteria is considered to be a Screen Failure. Screen Failure subjects will have their demographic information captured in the appropriate CRF with the reason for screen failure specified. No other information will be collected or analyzed. Since this is a pilot study, the analysis will be conducted on 10 subjects on each arm. If a

[figure not shown]
screen failure occurs, the investigator will need to continue to consent, randomize, and enroll until the 10 subjects for each arm is completed. A second set of randomization envelopes will be used for the recruitment of these screen failed subjects.

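### Match-and-replace from a second envelope set, filling each arm to 10 in an open-label single-site trial, does not secure allocation concealment for replacement subjects

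*Combined protocol and SAP*

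**What the plan says.** Section 9.1 names one specific protection against bias: "The randomization will be conducted via sealed envelope". Sections 10.6, 11 and 12.1 then set a separate rule for replacements.

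- **12.1:** "A match and replace method will be used to ensure that screen failed randomized subjects will be replaced appropriately". It adds: "The randomization assignment methodology will be documented in the Statistical Analysis Plan". Section 16, the statistical section of the combined document, describes no assignment method.
- **10.6:** after a screen failure the investigator is to "continue to consent, randomize, and enroll until the 10 subjects for each arm is completed", and "A second set of randomization envelopes will be used for the recruitment of these screen failed subjects".
- **Section 11:** if a subject cannot complete for any reason, "then the investigator will use the screen failed randomization envelope to recruit for this discontinued subject". It extends the same method further: "Any subjects in section 12 described below will be replaced using the method mentioned in this paragraph".
- **10.5:** the investigator may randomize before the baseline ultrasound, and that ultrasound can still make the subject a screen failure.
- **12.2 and the synopsis:** there is no blinding, and there is one center.
- **10.7:** 24 subjects are to be recruited, 12 per arm, with 10 per arm planned for analysis.

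**The concern.** Allocation concealment means that whoever decides on a patient's entry cannot foresee the assignment. In an open-label trial at one site, staff know each lost subject's arm and how many subjects each arm still needs. A rule that restores each arm to a fixed count turns that knowledge into a forecast of the next device.

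At stake is the comparability of the arms. Staff who can foresee the device can, knowingly or not, influence who enters under it. In arms of 10 to 12, a few selected subjects can move the primary thrombosis rate, and no later analysis reliably removes the resulting bias. The rule covers discontinued subjects as well as screen failures, so it can apply throughout the study.

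**Working it through.** **1. The plan's own figure.** 10 per arm plus 4 extra gives 2 × 10 + 4 = 24 = 2 × 12, as in 10.7. The implied allowance for loss is 4/24 = 16.7%. There is no power calculation to reproduce (16.2).

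**2. How well the site can predict a replacement's arm.** Let *a* and *b* be the numbers still needed in the two arms, both known to the site. Three readings of the rule are possible.

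*(i) The replacement takes the lost subject's arm.* Prediction is 100% correct.

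*(ii) Concealed 1:1 envelopes, with each arm closed when full.* Let B(a,b) be the expected number of correct guesses. If one arm is full, every remaining assignment is forced, so B(a,0) = a and B(0,b) = b. Otherwise B(a,b) = 0.5 + 0.5 × [B(a−1,b) + B(a,b−1)].

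- B(1,1) = 0.5 + 0.5 × (1 + 1) = 1.5
- B(2,1) = 0.5 + 0.5 × (1.5 + 2) = 2.25
- B(2,2) = 0.5 + 0.5 × (2.25 + 2.25) = 2.75
- B(3,1) = 0.5 + 0.5 × (2.25 + 3) = 3.125
- B(3,2) = 0.5 + 0.5 × (2.75 + 3.125) = 3.4375
- B(3,3) = 0.5 + 0.5 × (3.4375 + 3.4375) = 3.9375

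| Still needed (a, b) | Correct guesses / assignments | Predictable |
|---|---|---|
| (1,0) or (2,0) | all | 100% |
| (1,1) | 1.5 / 2 | 75% |
| (2,1) | 2.25 / 3 | 75% |
| (2,2) | 2.75 / 4 | 69% |
| (3,3) | 3.9375 / 6 | 66% |
| (3,1) | 3.125 / 4 | 78% |

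If the set instead holds exactly the missing assignments in shuffled order, the corresponding figures are similar: 75% for (1,1), 71% for (2,2) and 68% for (3,3).

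*(iii) A concealed second list used in order, with no cap per arm.* The first envelope is 50% predictable, which is chance. The concern would not hold under this reading, but the instruction in 10.6 to fill each arm to 10 points away from it.

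**3. How many subjects are affected.** The documents give no rate of loss after randomization, so the rates *f* are assumptions. Expected replacements to reach N are N × f/(1 − f).

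| Assumed f | To reach 24 | To reach 20 |
|---|---|---|
| 5% | 24 × 0.05/0.95 = 1.3 | 1.1 |
| 10% | 24 × 0.10/0.90 = 2.7 | 2.2 |
| 20% | 24 × 0.20/0.80 = 6.0 | 5.0 |
| 30% | 24 × 0.30/0.70 = 10.3 | 8.6 |

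At 10%, the chance of at least one loss among the first 24 is 1 − 0.9^24 = 92%. The rule would very likely be used.

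**4. Possible effect on a rate (illustration only).** If *r* of 10 subjects in an arm are replacements whose risk differs by *d* through selection, the arm's rate shifts by r/10 × d. One subject and 10 points gives 1 point; three subjects and 30 points gives 9 points. Both inputs are assumptions.

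**The case against.** A reader might infer that replacements' devices are known before anyone is approached, and that these subjects are not effectively randomized. The documents do not establish that. The matching is undefined, and nothing says the second envelopes are labelled by arm. Section 10.6 puts consent before randomization. Section 8.1 says any patient receiving a single lumen PICC will be approached, 10.1 says all such patients are screened, and 10.2 logs refusals. The method is deferred to the SAP, and figures missing from the available text of 10.5 and 10.6 may describe the envelopes. A missing figure is not a defect in the plan.

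These points limit the concern without removing it. Consent before opening the envelope gives no protection if the arm can already be foreseen. Approaching every patient narrows selection, but exclusions 9 and 10 rest on the opinion of the investigator and clinical staff, so discretion remains. A separate SAP could specify the envelopes, but it would have to depart from the protocol's stated matching and per-arm filling to restore concealment.

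A reader might also count forced assignments over the whole trial, as if all 20 or 24 subjects were allocated by coin toss until each arm is full. The documents describe no such scheme, so that count does not measure this problem.

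The pilot setting also counts. The study is unpowered (Section 8) and not intended to support claims (16.1). The illustrative shifts of 1 to 9 points are smaller than the sampling error of an arm of 10: at the 48% asymptomatic rate cited in 6.1, √(0.48 × 0.52/10) = 0.158, about 16 points. This limits the consequence. It does not excuse the rule, because the arms will still be compared by a trend test and Fisher's exact test (16.5.1), and neither allows for selection.

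**Conclusion.** The concern holds in conditional form. As written, the replacement rule does not secure concealment. The device is certain if replacements are matched to the lost subject's arm or if only one arm is short. It is predictable about 66-75% of the time for equal or near-equal shortfalls of up to three per arm, and 78% for shortfalls of three and one. Only a concealed list with no per-arm cap would avoid this, and the stated target per arm argues against that reading.

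About 3-10 subjects would be exposed on the way to 24, assuming 10-30% loss after randomization. The direction and size of any resulting bias cannot be derived from the documents. The rule should be changed before recruitment; it does not by itself invalidate a feasibility pilot.

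**What to change.** In 10.6, Section 11 and 12.1, remove arm-matched replacement, the separate second envelope set and the instruction to recruit until each arm is full. Replace them with:

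- one concealed, sequentially numbered list in randomly varied blocks, with spare envelopes; 24 + 10 = 34 would cover the expected need at 30% loss, and a margin beyond that is sensible;
- the next unopened envelope for every additional subject, whatever arm was lost and for whatever reason;
- a stop at a fixed total set in advance, for example the 24 enrolled subjects of 10.7.

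If the sponsor prefers to keep a second set, stating its content, order and custody, with no arm matching and no per-arm cap, would also answer the concern.

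The cost is a wording change and a longer list. Arms may end slightly unequal. With uneven losses one arm could fall a little below 10 evaluable subjects: three losses from an arm of 12 leave 9. That is acceptable in a pilot with no power target. Varied blocks reduce predictability in an open-label trial but do not abolish it, so block sizes should be withheld from the site.
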